5.12 EATING BETWEEN FEEDING PERIODS

Participants are counselled to maintain a similar lifestyle during the periods between study feeding so that weight remains stable. Fig. 5.12.1 is an example of a printed instruction to be given to the participant.

Figure 5.12.1 Guidelines for Between Feeding Periods

DELTA Guidelines for Between Feeding Periods

Between diet periods, it is important to maintain your weight and lifestyle habits. A change in weight of more than three-four pounds and/or a change in lifestyle habits could affect the results of the DELTA study. Since weight and lifestyle habits maintenance are two top priorities, the following guidelines have been prepared to help you achieve these goals.

Weight

1. Eat a wide variety of foods and limit the use of large amounts of fats and concentrated sweets.
2. Weigh yourself on a weekly basis. If you gain more than two pounds within a week, you will find these tips helpful in controlling your weight.
 - Eat generous portions of starchy foods like bread, rice, pasta, cereals, beans, and potatoes. Prepare and eat these foods with little or no added fat.
 - Eat plenty of fruits and vegetables. Prepare and eat these foods with little or no added fat and/or sugar.
 - Eat moderate portions of lean meat, fish, and poultry (remove poultry fat and trim visible fat from meat). A moderate portion is no more than four-six oz. of meat, fish, or poultry each day.
 - Use salad dressing or oil in moderation (1-2 TB/day). Use fat-free dressing if you need more.
 - Use fat spreads such as butter, margarine, cream cheese, and mayo-type dressing in moderation (1-2 tsp/day).
 - Avoid deep fried foods, cream sauces, cheese sauces, gravy, regular ice cream, and rich desserts or limit them to once each week.
 - Drink skim or 1% milk instead of 2% or whole milk. Use milk instead of cream in your coffee.
 - Limit alcohol use to one -- two drinks per week.
3. Weight loss is seldom a problem between diet periods. However, if you lose more than three-four pounds, increase your portion sizes at meals and include snacks liberally.

Lifestyle

1. If you are not smoking, please do not start.
2. Plan to maintain your current level of physical activity. A decrease in an activity should be replaced by an increase in a comparable activity. Avoid beginning new activity routines that result in a major change in either intensity or duration.

If you have any questions or concerns regarding your weight, food intake, smoking and physical activity, please call _____ at _____.

HAVE A WONDERFUL BREAK!!

See you for dinner (Month, Day)

APPENDIX I:
DELTA - 2 DIET FORMS

Instructions Food Production Form (FPF)

The Food Production Form (FPF) is used in conjunction with the RECIPES for portioning all menu items. There is a separate FPF form for each diet and menu. The forms are color coded (Green: Diet D, Buff: Diet E, Salmon: Diet F).

1. **Prepare the Food Production Form:** Fill in the date corresponding to the menu that will be served. Menu sequence is shown in the Manual of Procedures, pages 28-35.

Circle the day of the week corresponding to the date.

Count the number of participants receiving each calorie level for the corresponding diet and fill in this number in the box above each calorie designation.

2. **Portion the items as listed in the food production sheet:** When all the portions for a given item have been weighed/portioned out, the staff responsible will initial the item.

FOOD PRODUCTION FORM

DIET D MENU 1

DATE:       mm dd yy	Staff Initials					
DAY: M T W T F S S		1500	2000	2500	3000	3500
BREAKFAST						
Orange juice		124.0	124.0	124.0	124.0	248.0
Triples		23.0	23.0	23.0	46.0	46.0
White Bread (PF)		22.7	45.4	90.4	90.4	90.4
Butter		8.0	9.0	15.0	20.0	20.0
Sweets; jellies		0.0	10.0	10.0	10.0	10.0
Jellies, dietetic		14.2	0.0	0.0	0.0	0.0
Milk, whole		245.0	245.0	245.0	490.0	490.0
LUNCH						
Sandwich package:						
*Turkey breast meat		35.0	50.0	56.7	56.7	75.0
*Mayonnaise, regular		4.3	5.0	6.0	9.0	9.0
*Iceberg lettuce		0.0	0.0	0.0	10.0	10.0
*White bread (PF)		45.4	45.4	45.4	45.4	90.8
Iceberg lettuce		24.0	24.0	24.0	40.0	40.0
Olive oil		0.0	2.0	2.0	10.0	8.0
Peaches, juice pack		127.6	127.6	127.6	127.6	127.6
Ginger Cookie		14.0	22.0	22.0	22.0	22.0

Instructions Tray Assembly Check Sheet (TAC)

The Tray assembly Check Sheet (TAC) is filled out each day for all participants in the study. There are separate forms for each calorie level, each menu and each diet (total 150). The forms are color coded by diet (Green: Diet D, Buff: Diet E, Salmon: Diet F).

1. **Prepare the form:** Select the menu corresponding to the date on which it will be served. Check the Manual of Procedures, pp 28-35 for the correct menu designation. Record the DATE on the TAC corresponding to the day it will be served and circle the corresponding DAY.

Write in the Name or DELTA ID for each participant on the corresponding diet/calorie TAC.

2. **Assemble the tray:** Verify the diet and calorie level of the participant with the portioned items. Then place each item on the tray as listed on the TAC. When the tray is assembled, check off each item in the corresponding box for that participant to verify that all items are provided and enter your (staff) initials.

Follow a similar procedure for packed meals, checking off each item as it is placed in the bag/ cooler, and initialing the completed meal assembly.

TRAY ASSEMBLY CHECK SHEET

Form Code: TA
Version A 9/15/9

DIET D	MENU 1	1500 KCAL					
DATE:    mm dd yy DAY: M T W T F S S CENTER: _____	NAME OR DELTA I.D.						
BREAKFAST							
Orange juice							
Triples (1 PC)							
White bread (1 slice)							
Butter							
Dietetic jelly (1/2 oz.)							
Whole milk (1 PC)							
Staff Initials							
LUNCH							
Turkey sandwich package							
Salad							
Salad Dressing							
Peaches (1 PC)							
Ginger Cookie (1 small)							
Staff Initials							
DINNER							
Sirloin Tips With Gravy							
Corn							
Salad							
Salad Dressing							
Rolls (1)							
Butter							
Applesauce, unsweetened (1 PC)							
Staff Initials							
SNACK							
Trail Mix							
Staff Initials							

Instructions

Participant Food and Beverage Intake Report Form (FBI)

Purposes:

1. To record the number of unit foods eaten and alcoholic beverages consumed so that total calories may be computed.
2. To compute a compliance score for deviations from the diet protocol.

Step 1: Prepare the form. Fill in the name, DELTA ID, day, date (that the B, L, D, S is eaten) and center. The participant will be completing the form for the time beginning **AFTER** the previous nights dinner through the end of the dinner meal being eaten.

Step 2: Place the form FBI on the participant's tray at dinner each day.

Step 3: Instruct the participant to fill in the form for the food and beverage they consumed since dinner on the previous night through the end of the meal being eaten.

Step 4: Retrieve the form at the end of the meal when the tray is returned. Resolve any questions at the next meal service.

Step 5: Code the form. Convert amount of alcohol into number of drinks. 12 oz. beer, 3 oz. dry wine, 1 shot (45 ml) hard liquor = 1 drink. Enter the number of drinks.

Calculate the kcal in the food not eaten and enter. If the total kcal > 100 , enter 2 on the code line for question 3. If the kcal ≤ 100 , enter 0.

Calculate the kcal in food reported in question 4 and enter. If the kcal > 100 , enter 2 on the code line for question 4. If it is ≤ 100 kcal, enter 0.

Step 6: Transfer the information from form FBI to form CCS for the corresponding day.

Participant Food and Beverage Intake Report

Please complete this form each day and return it to the DELTA kitchen staff or Study Coordinator.

Name _____ DELTA ID # _____

Date: ____ / ____ / ____
mm dd yy

1. How many unit foods did you eat on this day?
2. Did you drink any alcoholic beverages on this day?
 No Yes If yes, list.

Specify type (Beer, Wine, Hard Liquor, etc.)	Amount	# Drinks <small>(For administrative Use)</small>

Total _____

3. Were there any study foods you did not eat/drink on this day?
 Reasons include missing, spilled, or inedible food, illness or other.
 No Yes If yes, list.

Food	Amount	Reason	Kcal <small>(For administrative use)</small>

Total Kcal _____

4. Did you eat anything other than study foods or drink more than 5 caffeine containing beverages on this day?
 No Yes If yes, list.

Food or Drink	Amount	Kcal <small>(For administrative use)</small>

Total Kcal _____

Instructions for completing the DELTA Diet Deviation Form (DDD)

Purposes: To provide a record of deviations observed during on-site meal service, and to record deviations called in to DELTA staff members during weekends.

For on-site deviations:

Step 1: Check the meal tray. If any study food or beverage is left, fill in a DDD. All other information on deviations is obtained from form FBI filled out by the participant). If there are discrepancies between observations by the kitchen staff and information reported by the participant on the FBI, those should be adjudicated by the dietitian before filling in the CCS.

Step 2: If food is not eaten by the end of the day, calculate the kcal value of the food and enter in question 3 of the DDD. This information will be used for calculating the compliance code.

For deviations called in during weekends:

Step 1: Fill in a DDD if a participant calls a DELTA staff member to report a deviation during a weekend (ex. missing, lost, spoiled food). All other information on deviations is obtained from form FBI filled out by the participant). If there are discrepancies between observations by the kitchen staff and information reported by the participant on the FBI, those should be adjudicated by the dietitian before filling in the CCS.

Step 2: If food is not eaten by the end of the day, calculate the kcal value of the food and enter in question 3 of the DDD. This information will be used for calculating the compliance code.

DELTA DIET DEVIATION FORM

To be used by kitchen personnel for reporting ON-SITE and WEEKEND packed meal deviations ONLY!

Name of participant: _____

D E L T A I D :

Date of deviation: ___ / ___ / ___
B L D S
mm dd yy

Day: M T W Th F Meal:

1. List the food/beverage left on the tray and the amount (for on-site meals) OR List the items and amounts that participants called the DELTA Staff member about (for weekend meals).

2. What was done with the food?

- a) Given back to the participant to eat? YES NO
- b) Replaced at the next meal and eaten? YES NO
- c) Given back/replaced, but still not eaten? YES NO
- d) Not replaced, therefore not eaten? YES NO
- e) (Weekend) replaced with non-study food? YES NO
- f) Other, describe _____

3. What was the kcal value of the uneaten or non-study food?

--	--	--	--

Instructions DELTA Compliance Check Sheet (CCS)

Purpose:

The DELTA Compliance Check Sheet (CCS Version A) has four purposes:

1. To document meal by meal that all study food provided was consumed, or if not consumed to document the deviations.
2. To record the number of unit foods consumed.
3. To record the number of alcoholic beverages consumed.
4. To record a compliance code.

Step 1: Prepare the CCS. Write in the Center name and the date when the food is to be eaten. Enter each participant's name and DELTA ID number.

Step 2: For on site meals, check the breakfast tray to assess whether any food was left. If all study food and beverage were eaten, enter N in the B (Breakfast) column. If food was left, enter D in the B column and fill in a DELTA Diet Deviation form (DDD).

Repeat this step for each participant.

Enter the personnel code or initials of the person checking breakfast.

Step 3: Repeat step 2 for lunch. If breakfast or lunch was a packed meal, refer to the corresponding Participant Food and Beverage Intake Report (form FBI) question 3. If question 3 was answered No, then enter N in Column L (Lunch or B for packed breakfast). If question 3 was answered Yes, enter D in column L (or B).

Step 4: Each participant will be given an FBI form to complete for the previous 24 hours. Repeat step 2 for dinner.

Step 5: Refer to form FBI for information on snacks and enter either N or D in column S (Snack).

For weekend packed meals, refer to the FBI Form for information for filling in columns B, L, D, S.

Instructions

DELTA Compliance Check Sheet (CCS)

Step 6: Refer to form FBI, question 1 and fill in the number of unit foods eaten. Enter the personnel code for the person filling in this column.

Step 7: Refer to form FBI, question 2, and fill in the number of alcoholic beverages reported. Enter the personnel code for the person filling in this column.

Step 8: Compute the total kcal value of deviations from form FBI and the deviation form (if any). Enter the total in column "Total kcal of deviations."

The total value is the sum of negative and positive values, e.g., 1 piece of bread (70 kcal) not eaten at breakfast, and a small apple (80 kcal) eaten in addition to study foods would = 150 kcal worth of deviations.

If more than 5 caffeine containing beverages were consumed in one day, notify study coordinator.

If there is a discrepancy between question 3 from FBI and the deviation form, it must be resolved with the participant before completing form CCS.

Step 9: Check the form carefully to be sure all information has been completed correctly before the form is sent for keying.

page 2

COMPLIANCE CHECK SHEET

FORM CODE: CCS
VERSION A: 10/25/94

CENTER ID: C20000

TODAY'S DATE: ___ / ___ / ___

(1)	Participant Name (Mask all participant names before sending this form to the Coordinating Center.)	DELTA I.D. No. (2)	Any food or beverages left? Enter N for none, D for deviation.				# of Unit Foods (from FBI form) (3)	# of Alc. bev. (from FBI form) (4)	Total kcal value of deviation (from deviation form) (5)
			B	L	D	S			
1.									
2.									
3.									
4.									
5.									
6.									
7.									
8.									
9.									
10.									
11.									
12.									
13.									
14.									
15.									
Personnel code # or Initials ▶									

Shaded area must be keyed into the DELTA DMS

TURN OVER FOR SIDE 2 ▶

COMPLIANCE CHECK SHEET

CENTER ID: C20000

(1)	Participant Name (Mask all participant names before sending this form to the Coordinating Center.)	DELTA I.D. No. (2)	Any food or beverages left? Enter N for none, D for deviation.				# of Unit Foods (from FBI form) (3)	# of Alc. bev. (from FBI form) (4)	Total kcal value of deviation (from deviation form) (5)
			B	L	D	S			
16.									
17.									
18.									
19.									
20.									
21.									
22.									
23.									
24.									
25.									
26.									
27.									
28.									
29.									
30.									
Personnel code # or Initials ▶									

Shaded area must be keyed into the DELTA DMS

Instructions DELTA Packed Meal (PMF) and Snack Forms

The **DELTA PACKED MEAL (PMF)** form and/or the **SNACK** form will be used for all carry out foods. These forms are a check list for the participant to verify what items have been packed in their carry out containers.

Before filling in the form, first verify that the menu number matches the corresponding menu number on the **TAC**.

Enter the first and last name of the participant, ID number, day and the date on which the food will be eaten.

Kitchen personnel will check off each item as it is put into the container or bag, and enter the packers code number. Before attaching the PMF to the container, be sure to cut off the corner identifying the diet. A Fresh-Check™ Time-Temperature Indicator (TTI) label will be placed in each cooler or bag that the participant takes off site. Each Participant will be given a copy of the TTI instruction sheet and instructed on food safety.

The **PMF** and/or **SNACK** form will be attached to the container. Instruct the participant to contact a DELTA staff member if any item checked off on the form is missing from the container.

Snack Form

Menu 1

Name: _____ ID: _____ Day: _____

Date: ___ / ___ / ___ Packed by: _____ Contact Tel. #: ___ - ___ - ___
mm / dd / yy

Packed

- Trail Mix
- _____
- _____
- Free beverage

NOTE: If any part of your snack is missing or inedible be sure to note it on your Food and Beverage Intake Record for the day.

Snack Form

Menu 1

Name: _____ ID: _____ Day: _____

Date: ___ / ___ / ___ Packed by: _____ Contact Tel. #: ___ - ___ - ___
mm / dd / yy

Packed

- Trail Mix
- _____
- _____
- Free beverage

NOTE: If any part of your snack is missing or inedible be sure to note it on your Food and Beverage Intake Record for the day.

PACKED MEAL FORM

D

MENU 1, 1500 Kcal

Name _____ I.D. _____ Telephone Contact () _____

Day M T W T F Other _____ Date _____ Packed by _____
(Circle One) (Specify) mm dd yy

BREAKFAST	LUNCH	DINNER
Packed  Orange juice  Triples (1 PC)  White bread (1 slice)  Fat spread  Dietetic jelly (1/2 oz.)  Whole milk (1 PC)  Free beverage	Packed  Turkey sandwich package  Salad  Salad Dressing  Peaches (1 PC)  Ginger Cookie (1 small)  Free beverage	Packed  Sirloin Tips with Gravy  Corn  Salad  Salad Dressing  Rolls (1)  Fat spread  Applesauce, unsweetened (1 PC)  Free beverage

UNIT FOODS	SNACK
# of Units Packed  Roll  Pumpkin muffin  Banana muffin  Corn muffin _____ _____ _____ _____	Packed  Trail Mix

Chicken Jambalaya

Diet D

Menu #2

Batch	1500	2000	2500	3000	3500
	Rice, white, cooked and cooled	69.0	92.0	115.0	115.0
Tomato sauce	24.0	32.0	40.0	40.0	48.0
Onions, diced	8.0	10.5	13.0	13.0	16.0
Green peppers, diced	8.0	10.5	13.0	13.0	16.0
Celery, diced	7.0	9.5	12.0	12.0	14.0
Garlic, minced	1.1	1.4	1.7	1.7	2.0
Sugar	0.6	0.8	1.0	1.0	1.2
Spice mix (salt, black pepper and parsley flakes ⇒ proportion = 8:1:1)	1/2 tsp	1/2 tsp	3/4 tsp	3/4 tsp	1 tsp
Tabasco sauce					
WEIGHT OF BATCH SERVING:					
	117.7	156.7	195.7	195.7	235.2
Batch Method: Combine rice, tomato sauce, onions, green peppers, celery, garlic, and sugar. Mix well. Portion into individual serving dishes. Add spice mix and 1-2 drops tabasco sauce to each serving. Fold to mix.					
Add to each serving:					
Egg yolk, dried	5.0	2.5	1.0	---	---
Chicken, breast meat, raw, cubed, patted dry with a paper towel	53.0	71.0	82.0	89.0	130.0
Lard	8.5	11.0	11.0	---	---
Coconut oil	8.5	11.0	12.0	27.5	36.0
Individual Method: Add cubed chicken, lard, coconut oil and egg yolk to individual portions. Mix well.					
Cooking Method: Bake uncovered in a preheated oven at 325° F for 20-25 minutes. (Convection 300° F for 15-20 minutes).					

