3.6.1 Eligibility Visit 1 Form

Eligibility Visit 1

Form Code: EV1
Version B 5/10/94

4. What is your highest level of education completed? [Please circle the letter preceding your selection.]

- A Eighth grade or less
- B Trade school or business school instead of high school
- C Some high school
- D High school graduate
- E Trade school or business school after graduating from high school
- F Some college including 2-year degree
- G Received bachelor's degree
- H Graduate or professional education beyond the bachelor's degree
- I Graduate or professional degree

5. a. What is your current employment status? [Please circle the letter preceding your selection.]

- A Working a full-time job
- B Working a part-time job
- C Full-time or part-time student, not working
- D Student working full-time or part-time
- E Homemaker/Volunteer
- F Retired
- G Unemployed
- H Disabled
- I Other

b. If Other, describe: _____

6. Do you plan to remain in the area for the next year? [Circle answer] YES NO

Eligibility Visit 1

Form Code: EV1
Version B 5/10/94

7. Do you have any allergies or sensitivities to any of the following foods? [Read each of the following foods and circle your response YES (Y), NO (N), or UNSURE (U)]

a. meat, fish or poultry	Y	N	U
b. shellfish	Y	N	U
c. milk or dairy products	Y	N	U
d. If, YES to milk or dairy products, is this a milk allergy?	Y	N	U
e. If YES to milk or dairy products, is this a lactose intolerance?	Y	N	U
f. eggs	Y	N	U
g. fruit	Y	N	U
h. vegetables	Y	N	U
i. nuts	Y	N	U
j. chocolate	Y	N	U
k. other foods	Y	N	U
If YES to Other foods, list below: l. _____, m. _____, n. _____			

8. Are there any foods that you absolutely won't eat? [List each separately.] a. _____ b. _____ c. _____

Eligibility Visit 1

Form Code: EV1
Version B 5/10/94

We would like to ask you a few questions about your alcohol consumption...

DEFINITION: 1 drink = a 5 oz. glass of wine, a 12 oz. can of beer, or 1.5 oz. of liquor.

9. What is the total number of alcoholic drinks that you drink Monday through Thursday? _____
10. What is the maximum number of alcoholic drinks that you usually drink in any one day Monday through Thursday? _____
11. What is the total number of alcoholic drinks that you drink Friday, Saturday, and Sunday? _____
12. What is the maximum number of alcoholic drinks that you usually drink in any one day Friday, Saturday, or Sunday? _____

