4.0.1 Instructions for Drop-Out Form

Instructions for Completing the Drop-Out Form

The Drop-Out Form will be completed at the time that a randomized participant drops out of the study for any reason. Data from this form will be entered into the data management system.

DELTA ID AND TODAY'S DATE

Apply the pre-printed DELTA ID label or write in the 5-character ID number.

Record the date the form is being completed as month/day/year using leading zeros to fill in all spaces.

Question 1: Date of Last Visit

Record the date of the participant's last visit to the study site. Enter the date as month/day/year using leading zeros to fill in all spaces.

Question 2: Participant's Name

Record the participant's first name, middle name, and last name in 2a-c, respectively.

Question 3: Reason for Drop-Out

Circle only one letter corresponding to the reason for drop out from the study.

Question 4: Detailed Reason for Drop-Out

Describe the reason for drop-out in the space provided, write legibly and avoid abbreviations.

Question 5: Personnel Code Number

Record the personnel code number assigned to the DELTA study staff for the person completing this form.

Drop Out Form

Form Code: DPO
Version B 6/30/94

DELTA ID: _____

Today's Date ___ / ___ / ___

1. Date of last visit: _____
(mm/dd/yy)

2. a. First name: _____

b. Middle name: _____

c. Last name: _____

3. Reason for drop-out (circle only one):

- A Failure to comply with protocol (missing 2 meals, eating 3 self-selected meals greater than 40% fat, exceeding alcohol limits more than 1 time in a period)
- B Serious illness or death
- C Voluntary withdrawal

4. Any comments? Y [Yes] N [No] [Circle answer.] If Y, enter detailed reason or comments below:

5. Personnel code number: _____

Figure 4.0.1.1: Drop Out Form

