6. **Caffeinated beverages are limited to 5 cups of coffee per day or the equivalent, as listed:**

Coffee: up to 5 cups per day (1 cup = 6 oz.)

Instant coffee: up to 9 tsp per day

Brewed Tea: up to 10 cups per day (1 cup = 6 oz.)

Instant Tea: up to 16 tsp per day

Diet Soda Pop: up to 5 caffeinated cans per day (1 can = 12 oz.)

(Examples: Diet Coke, Diet Cherry Coke, TAB, Diet [name], Diet Rite Cola, Diet 7-Up Gold, Diet Pepsi, Diet Mountain Dew, Diet Mello Yello)

Non-caffeinated diet or unsweetened beverages may be consumed in any amount desired.

Alcoholic Drinks: limited to no more than 5/WEEK

(1 drink = 5 oz. wine, 12 oz. beer, or 1 1/2 oz. shot glass of liquor. Liquor must be mixed with only those beverages that are allowed.) **NO ALCOHOLIC DRINKS ARE PERMITTED 48 HOURS BEFORE BLOOD DRAWING.**

7. In case of emergency situation, please call the following numbers in order:

[name], Project Coordinator	[name](Home: [name])
[name], Research Assistant	[name](Home: [name])
[name], Research Dietitian	[name](Home: [name])
Dining Room	[name]
Kitchen	[name]

ANY QUESTIONS?? Always feel free to ask DELTA staff.

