5.6 FEEDING

All centers will serve two meals a day Monday through Friday at the feeding site. **One of the meals must be dinner.** Meals not eaten at the center, snacks and free beverages will be packaged in suitable leak-proof containers for consumption off site (see Food Safety; pages 59-62). Participants must eat and drink all study foods provided except for discretionary items (see next section). Participants should be given instruction in how to use either bread or a rubber spatula to be sure they consume all food residues. Rubber spatulas should be provided for home use.

5.6.1 Discretionary foods, beverages and seasonings:

Discretionary foods

1 - 2 TBSP fat free salad dressing/day

Up to 2 c. iceberg lettuce/day

1 tsp. mustard/day

Fat-free Salad Dressings are interchangeable

Discretionary beverages

A limited number of alcoholic and caffeinated beverages are allowed. Alcoholic beverages may be consumed up to 5 drinks per week. One drink is defined as:

1 shot (1.5 oz.) hard liquor

1 - 12 oz. can of beer

1 - 5 oz. glass of dry table wine

Cordials (liqueurs) and mixed drinks containing sugar are not permitted.

No alcoholic beverages are permitted 48 hours prior to blood drawing.

Caffeinated beverages not containing sugar may be consumed in amounts up to the following limits:

5 (6 oz.) cups coffee or tea

5 12 oz. glasses iced tea

5 12 oz. cans diet soda: Diet Coke, Diet Cherry Coke, Diet 7-UP Gold, TAB, Diet Rite Cola, Diet [name], Diet Cherry Cola, Diet Pepsi, Jamaica Cola, Canada Dry, Mountain Dew, Mellow Yellow

Non-caffeinated diet or unsweetened beverages may be consumed in any amount.

Sugar-free, calorie-free chewing gum is allowed.

Discretionary seasonings:

The following seasonings are allowed for discretionary use: salt, pepper, [name], Seasoned salt, Lemon pepper, Tony's (Louisiana), Tabasco or other red pepper sauce, vinegar, lemon juice, and soy sauce limited to 1 portion pack per day.

The following seasonings are not allowed for discretionary use: Worcestershire or similar steak sauces containing fermented products and/or anchovy.

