APPENDIX II:
ADDITIONS and REVISIONS

To: [name]
From: [name]
Date: September 26, 1994

Pumpkin Unit Foods:

We had several complaints during the Diet Run-In on the Pumpkin Unit Muffins. They were described as bland and tasting like cardboard. Increasing the cinnamon and/or using a pumpkin pie spice mix instead of the cinnamon, may improve the acceptability of this product. I checked to see how significant an increase in the spices would be. Doubling the amount of cinnamon would be an increase of 3 grams for the batch totaling 1494 grams of product. This is a .2% increase in the total batch size, and individual muffins would be affected by 0.1 gram which would probably not require an increase in the muffin size. Each center may want to try these suggestions and make adjustments based on regional tastes.

Also - we received our potato & corn chips 

MOP Update - Chapter 5
10/24/94

Additional instructions for completing the FBI form:

Follow the standard rules for rounding when entering the number of alcoholic beverages consumed and # of unit foods eaten into the DELTA Data Management System (DMS). The initial version of the Food and Beverage Intake Record (FBI) only allows for a single digit with no decimal place entry into the Data Management System (DMS). Therefore:

These numbers should be rounded up or down to the nearest whole number when entering them into the DMS. Specifically, this means rounding numbers .4 and lower, down; and numbers .5 and higher, up to the nearest whole number. Both the exact number and the rounded number should be noted on the written form.

DELTA MEMORANDUM

TO: Study Coordinators and Dietitians/Diet Coordinators

COPIES TO: [name], [name] and [name]

FROM: [name] *LM*

DATE: February 22, 1995

SUBJECT: Allowances for Dietary Deviations (TO BE USED ONLY IF REQUESTED BY PARTICIPANTS) for the three Fridays in Feeding Period 3 that fall during Lent

In response to the request of three participants at Pennington, the following decisions have been made to address the needs of DELTA participants who do not want to eat meat on Fridays during Lent. Before I review the decisions that have been made to allow for this request, **LET ME EMPHASIZE AGAIN THAT THESE DEVIATIONS SHOULD ONLY BE ALLOWED IF THE PARTICIPANT INITIATES A REQUEST. THESE CHANGES ARE NOT TO BE OFFERED UNSOLICITED TO ALL PARTICIPANTS.**

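### The food and beverage form has staff code 3 oz of wine as one drink, while participants are told 5 oz, so keyed wine intake is overstated by a factor of 1.67

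*Protocol*

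**What the plan says.** One drink of wine is defined as 5 oz in five places in the protocol:

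- the telephone screening instructions (Section 3.3.3, question 33);
- the Telephone Screening Form itself;
- the Eligibility Visit 1 form (Section 3.6.1): "DEFINITION: 1 drink = a 5 oz. glass of wine, a 12 oz. can of beer, or 1.5 oz. of liquor";
- the Minnesota participant guidelines (Section 5.5.1): "1 drink = 5 oz. wine, 12 oz. beer, or 1 1/2 oz. shot glass of liquor";
- the feeding rules (Section 5.6.1): "1 - 5 oz. glass of dry table wine".

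The limit during feeding is in Section 5.6.1: "Alcoholic beverages may be consumed up to 5 drinks per week".

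The staff coding rule in FBI Step 5 (Chapter 5, Appendix I) reads differently: "12 oz. beer, 3 oz. dry wine, 1 shot (45 ml) hard liquor = 1 drink". Participants enter type and amount on the form, and staff fill in the number of drinks. Step 6 passes the result to the Compliance Check Sheet (CCS), whose Step 7 says: "Refer to form FBI, question 2, and fill in the number of alcoholic beverages reported". Section 5.7.3 states that the CCS is keyed. The FBI instructions give computing total calories as the reason for recording alcohol.

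The manual update of 10/24/94 (Chapter 5, Appendix II) adds, for drinks and unit foods: "These numbers should be rounded up or down to the nearest whole number when entering them into the DMS". Values of .5 and above go up, and the exact and the rounded number are both to be written on the form. The Drop-Out Form (Section 4.0.1) lists, under failure to comply, "exceeding alcohol limits more than 1 time in a period".

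**The concern.** Participants are told one size of wine drink and coded by a smaller one. Someone who follows the instructions exactly can therefore appear on the keyed record as exceeding the weekly limit. Two things are at stake. The first is the accuracy of the alcohol count, which is one of the items the CCS exists to document and which also enters the total-calorie calculation. The second is that the same record could be cited for a non-compliance drop-out, and in a three-period crossover a participant who leaves early contributes nothing to the later diets.

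**Working it through.** **Is the difference confined to wine?** Compare the Step 5 line with the stated definitions.

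| Beverage | FBI Step 5 | Stated definitions | Agree? |
|---|---|---|---|
| Beer | 12 oz | 12 oz | yes |
| Liquor | 45 ml = 45/29.57 = 1.52 oz | 1.5 oz | yes |
| Wine | 3 oz | 5 oz | no |

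Step 5 and Section 5.6.1 both specify dry wine, so the gap is not explained by a different kind of wine.

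**Inflation per glass.** Coded drinks = ounces / 3. One 5 oz glass gives 5/3 = 1.67, which is keyed as 2 under the rounding rule.

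**Where the coded limit falls.** 5 drinks × 3 oz = 15 oz a week, against 5 drinks × 5 oz = 25 oz as participants are told. The coded limit is 1 − 15/25 = 40% lower.

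**Weekly counts, wine only, 5 oz glasses:**

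| Glasses per week | Ounces | Coded at 5 oz | Coded at 3 oz, exact | Coded at 3 oz, one glass a day, rounded daily |
|---|---|---|---|---|
| 1 | 5 | 1 | 1.67 | 2 |
| 2 | 10 | 2 | 3.33 | 4 |
| 3 | 15 | 3 | 5.00 | 6 |
| 4 | 20 | 4 | 6.67 | 8 |
| 5 | 25 | 5 | 8.33 | 10 |

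**Dependence on spread.** The last column assumes single-glass days. Two glasses in one day give 10/3 = 3.33, keyed as 3.

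- Three glasses taken as 2+1 key as 3 + 2 = 5, which is not over the limit.
- Five glasses taken as 2+2+1 key as 3 + 3 + 2 = 8. All on one day they key as 8 (25/3 = 8.33). One on each of five days they key as 10.

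So the permitted maximum is keyed as 8 to 10.

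**Link to the drop-out wording.** Two weeks at the permitted 25 oz within one seven-week feeding period would show on the coded record as two breaches, which meets the more-than-once wording on the Drop-Out Form.

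**Check after alignment.** At 5 oz per drink, one to five glasses code as exactly 1 to 5, and whole glasses need no rounding.

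**The case against.** Several points on the other side are sound.

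- **Reach.** A reader might infer that every compliant wine drinker is recorded over the limit. The figures do not support that. Drinking wine only, one or two glasses a week code to at most 4, and three glasses are exactly 5.00 before rounding.
- **Size.** The figure of 10 drinks holds only for one glass on each of five days; other patterns give 8 or 9.
- **Removal.** A reader might also infer that the coded count causes participants to be dropped. No section says so. The Drop-Out Form records a reason once someone has left, and Appendix A (A.2.2) leaves involuntary withdrawal to the principal investigator after discussion with the Steering Committee.
- **Safeguards.** The form keeps type and amount as reported, and the 10/24/94 update keeps the exact count beside the rounded one, so the information needed to correct the record is retained on paper.
- **Bias between diets.** The rule is the same for all three diets and alcohol is not an endpoint. No distortion of the diet comparison is shown.
- **Calories.** No kcal-per-drink factor is given, so the size of the calorie error cannot be stated.

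It can also be said that the matter turns on one digit, which may be a copying slip. That is possible but not shown, and a slip in an operating instruction still produces wrong data if staff follow it. None of these points removes the conflict: before any rounding, 25 oz still codes as 8.33.

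**Conclusion.** The point stands as an internal contradiction in an operating rule. Following FBI Step 5 as written overstates wine intake by a factor of 1.67 relative to the definition participants are given. Participants who keep to the stated limit but drink more than 15 oz of wine a week, or one glass on each of three days once rounded, are recorded as over it. The consequence is an inflated alcohol count in the compliance and total-calorie data, plus a record that could be used to support a non-compliance drop-out. Systematic loss of participants and a biased diet comparison are not established.

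The figures assume 5 oz glasses, amounts that staff convert from ounces, and no other alcohol in the week. Someone who also drinks beer or liquor would reach the coded limit with less wine: two glasses and three beers are 5 drinks by the stated definition but 3.33 + 3 = 6.33 as coded. How many participants are affected cannot be derived from the protocol.

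**What to change.** 1. Reconcile FBI Step 5 with Section 3.3.3, the Telephone Screening Form and Sections 3.6.1, 5.5.1 and 5.6.1, so that staff code wine by the same definition participants are given. Check the printed page of Step 5 at the same time.
2. Recode any FBI and CCS forms already completed, using the type and amount entries retained on the FBI, and correct the keyed counts.
3. Judge the weekly limit on the sum of the exact numbers written on the forms, not on rounded daily values.
4. Review any drop-out already attributed to alcohol against the recoded record.

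The cost is one figure in a form instruction, a clerical recode and a short notice to the four centers. The data management system need not change: once the definitions match, whole glasses code as whole numbers, so a decimal field is unnecessary.
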